8.3.4. Treatment-related Outcomes

Treatment-related AEs (eg, hypertension, neutropenia, thrombocytopenia, fatigue, stomatitis) will be documented for the duration of first-line treatment with sunitinib. Frequency of toxicity evaluation (eg, every 6 weeks) and the method of evaluation (eg, radiological evaluations by computed tomography, magnetic resonance imaging with measurable lesions via Response Evaluation Criteria in Solid Tumors [RECIST]) will also be documented.

Dates of progression and death (ie, whether the patient died during the follow-up period and whether the death was related to RCC) will be documented. Disease progression and survival estimates will be derived from these measures and calculated from the date of diagnosis of metastatic RCC, the start of first-line treatment line with 4/2 or 2/1 sunitinib, and the time of switch to the 2/1 schedule (among those who initiated on the 4/2 schedule). Survival estimates will include, but are not limited to, the following:

[figure not shown]
- Overall survival;
- PFS;
- Time to second-line initiation.

8.4. Data Sources and Data Collection Method

Data will be abstracted from the medical records of patients at various treatment centers in the selected countries. This study is retrospective; therefore, the collection of data will in no way influence prescribing patterns or treatment decisions.

Medical record abstractions provide a unique opportunity to collect and analyze real-world data outside the highly controlled setting of clinical trials. Generally, medical record abstraction enables collection of detailed information on patient demographic and clinical characteristics, treatment patterns, and health outcomes that may otherwise be unavailable in a standardized manner. The use of medical record abstraction allows for the development of a highly customized CRF that meets the specific needs of this study.

PFIZER CONFIDENTIAL

While ethics activities at sites are ongoing, the CRF will be programmed into a web-based eCRF. Following ethics approval and finalization of the eCRF, PPD will send secure links of the eCRF to the PI or the designated study coordinator of each site. The PI and/or their designated research team will screen their patients' records to identify eligible patient records. Once a potential medical record is identified, the PI and/or their research team will answer multiple screening questions in the eCRF to confirm the selected medical record is eligible for inclusion. After the medical record is determined to be eligible, the PI and/or their research team will complete the eCRF form by retrospectively reviewing all available data in the medical record. See [Section 8.9](#) for a detailed review of the limitations of this study type. It is anticipated that it will take an abstractor approximately 30 to 45 minutes to complete the CRF for each patient record.

8.5. Study Size

A convenience sample of at least 150 medical record abstractions will be targeted across all sites and 7 Latin American countries. As this study is descriptive in nature, no formal power calculations were conducted to determine the sample size for this study. This study does not involve hypothesis testing (via statistical testing) and is primarily being conducted to understand clinical characteristics, sunitinib treatment patterns, and health outcomes.

It is anticipated that all participating sites will provide data for all eligible patients. If any site estimates a greater number of eligible patients than needed to meet the total study sample size in the respective country, that site will be required to select a quasi-random sample of eligible patients for the study. This process will entail selection of medical records for patients whose last names begin with a randomly generated letter between A and Z, provided to the abstractor during data collection. For example, if "M" is the randomly generated first letter and if the abstractor does not have any patients who meet the study criteria and whose last name begins with "M," then they will select a patient whose last name begins with the next letter in alphabetical order (in this example, "N"). Due to variations in the distribution of first letters among last names, patients may not have an equal probability of inclusion in the study.

The PIs will be responsible for meeting sample size expectations at their respective sites. In the event that sample sizes are not met with the selected sites, other sites with additional eligible patients may be asked to provide data for additional patients or new sites may be recruited. The anticipated sample size in each country will be fixed; however, the sample obtained from each participating site will vary, depending on the available sample.

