8.2. Setting

Data for this study will be abstracted from the medical records of patients treated for metastatic RCC at approximately 17 treatment centers (ie, sites) in 7 countries: Argentina, Brazil, Colombia, Costa Rica, Ecuador, Mexico, and Peru.

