8.9. Limitations

Retrospective medical record reviews are subject to the following general limitations:

- Patients selected for study inclusion represent a “convenience” sample, in that the records will be obtained from sites who are willing to participate in the study. Therefore, study findings may not be generalizable to the overall population of patients with metastatic RCC or sites where RCC is treated in the selected countries.
- All data captured in the eCRF will be limited to information available in the patients’ medical records held by the sites participating in the study. Information on health care services received outside the sites’ care setting that is not recorded in the medical record will be unavailable for this study (eg, treatment for AEs received through a separate hospital).
- To increase the chance of random selection of eligible medical records at sites that estimate a larger than needed eligible population, abstractors will be asked to select medical records for patients whose last names begin with a randomly generated letter between A and Z. Due to variations in the distribution of first letters among last names, patients may not have an equal probability of inclusion in the study.
- Data will be entered directly by each site’s research team or PI and therefore may be subject to entry errors and resulting inaccuracies in reporting. Although there will be data checks in place to improve internal consistency of the data, responses will not be validated against the patients’ medical records by an independent reviewer.
- This study is designed to describe characteristics and outcomes of patients who switched from the 4/2 to the 2/1 sunitinib schedule. Potential confounders, such as characteristics that prompt the switch and other possible time-dependent factors (eg, dose modifications and delays), are not comprehensively collected or controlled in this study design. Variability in timing of the switch from a 4/2 to a 2/1 schedule will affect the distribution of time-dependent outcomes after the switch (even in the absence of immortal-time bias), as some patients may switch “early” in their first-line therapy and others may switch “later.” Thus, causal inferences about the benefit of switching treatment schedules cannot be drawn.

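### The surname-letter rule for sites with surplus patients does not say which record to take when several patients share a letter, and roll-forward makes inclusion chances more unequal than the plan discloses

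*Combined protocol and SAP*

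**What the plan says.** Section 8.5 sets the target: "A convenience sample of at least 150 medical record abstractions will be targeted across all sites and 7 Latin American countries". Section 8.2 puts this at "approximately 17 treatment centers (ie, sites) in 7 countries". The default in 8.5 involves no sampling: "It is anticipated that all participating sites will provide data for all eligible patients". Sampling begins only when a site expects more eligible patients than its country's fixed sample needs; then "that site will be required to select a quasi-random sample of eligible patients for the study".

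The device is "selection of medical records for patients whose last names begin with a randomly generated letter between A and Z", with the letter given to the abstractor during data collection. If no eligible patient has that initial, "then they will select a patient whose last name begins with the next letter in alphabetical order". Section 8.5 adds a caveat: "Due to variations in the distribution of first letters among last names, patients may not have an equal probability of inclusion in the study". Section 8.9 repeats the rule ("abstractors will be asked to select medical records for patients whose last names begin with a randomly generated letter between A and Z") and the same caveat.

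The plan is silent on four points:
- which patient to take when several eligible patients share the letter;
- whether a new letter is drawn for each record or one letter serves the whole site;
- what happens after Z;
- whether a list of eligible patients, or a count of those not selected, is kept.

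**The concern.** The rule has two separate weaknesses, and the caveat covers only part of one.

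**Unequal chances.** Letters are drawn uniformly and surnames are not, which the plan says. It does not say that an empty letter hands its chance to the next occupied one, so a patient who follows a run of unused letters is favoured. This can happen even if every patient has a different initial. It distorts results only if surname is related to outcome, which the documents give no reason to assume.

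**Choice within a letter.** When several eligible patients share the letter, the rule stops short of naming one. The choice then rests with the investigator or site team, who hold the record. A preference for long, complete or easily abstracted charts would be related to follow-up and so to outcome. Section 8.9 states that entries are not checked against the source record by an independent reviewer, and no log of unselected patients would show the pattern.

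Treatment duration, PFS and OS are themselves the results of this descriptive study, so selection on follow-up would enter them directly, with no comparison or test needed.

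**Working it through.** The plan states no inclusion probability, so there is no figure to reproduce. The documents supply the rule, the target of 150 and about 17 sites (150/17 = 8.8 records per site on average). They give neither the number eligible per site nor the surname distribution, so both are assumed below.

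**Step 1: first pick, exact.** With a uniform letter and roll-forward (Z followed by A),

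P(patient picked first) = (1 + e) / 26 / n,

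where e is the number of empty letters immediately before the patient's letter and n is the number of eligible patients sharing that letter (choice within a letter taken as random).

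Assumed list of 20 eligible: G 4, M 3, R 3, C 2, P 2, and one each of A, D, L, S, V, Z.
- Patient L: H, I, J and K are empty, so e = 4 and n = 1. P = 5/26 = 0.192.
- Each patient M: e = 0 and n = 3. P = 1/26/3 = 0.013.
- Ratio: (5/26) / (1/78) = 15. This contrast does not depend on what happens after Z.

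**Step 2: roll-forward without shared initials.** Assume 20 patients with initials A to T, one each. With wrap-around, A also receives U to Z: P = 7/26 = 0.269, against 1/26 = 0.038 for every other patient. If a draw beyond T is redrawn instead, each has 1/20 on the first pick. Simulating 10 of 20 with a letter per record, the top inclusion chance is about 0.96 with the wrap and about 0.5 without it. The high value in this particular list therefore comes from the assumed wrap.

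**Step 3: whole sample and worst-case preference.** Simulation of the Step 1 list, sampling without replacement and with wrap. Equal-chance sampling of 10 from 20 would give 0.50 to everyone. The survival column assumes exponential survival and that the longest-surviving patient is taken whenever a letter offers a choice.

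| Reading of the rule (10 of 20) | Lowest to highest inclusion | Worst-case excess in mean survival |
|---|---|---|
| New letter per record | 0.30 to 0.90 | about 20% |
| One letter per site, then onward | about 0.38 to 0.62 | about 2% |

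With a new letter per record, about 48% of picks offer more than one candidate. With one letter, each letter is used up before the next begins, so choice affects who is included only at the last letter reached.

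**Step 4: sensitivity of the worst case.**
- 6 of 20 needed: about 27% (letter per record) or 6% (one letter).
- 17 of 20 needed, letter per record: about 7%.
- 10 of 20, letter per record, longest chart taken on only half of the shared-letter picks: roughly 10%.

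**Step 5: pooling.** Section 8.7 pools the switch samples across countries. If surplus sites supplied 30% of records (assumed) and other sites were unaffected with the same underlying mean, the pooled excess would be 0.30 × 20% = 6%, or 0.30 × 2% = 0.6%.

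**Step 6: other lists.** With 9 of 20 needed and flat, moderately skewed or strongly skewed initials, the median lowest and highest inclusion were about 0.15-0.18 and 0.84-0.90 (letter per record), or 0.20-0.29 and 0.61-0.70 (one letter). The equal chance is 9/20 = 0.45. Between 54% and 66% of patients shared an initial with another eligible patient.

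**The case against.** The strongest reply is that the rule is contingent and its weakness is largely admitted. Sites are expected to contribute every eligible patient; the letter applies only where there is surplus. Section 7 calls switching relatively new in these countries, and 8.5 also plans for shortfall. The plan does not present the sample as strictly random, states the unequal chances twice, and disclaims causal inference in 8.7 and 8.9. All of this stands. It limits how much of the study is exposed and makes it wrong to say that unequal probability was concealed. It does not cover choice within a letter: 8.9 explains convenience as the willingness of sites to take part, not as selection of patients inside a site.

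A second reply is that the large figures depend on the reading. The plural wording about records and patients allows one letter per site, under which the worst case nearly vanishes; the worked example, which speaks of selecting a patient, points the other way. This stands too, and is why both readings are given.

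A reader might infer that abstractors are given a free choice and will know the outcome when they choose. The documents do not say so. The freedom follows from silence, and 8.4 puts screening questions before full abstraction. However, screening itself requires the treatment dates, so the chart is at hand. A reader might also infer that nothing could be corrected afterwards. That is too strong: letter-driven chances could be computed if the initials of all eligible patients were kept. Only discretionary choice would be beyond repair.

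**Conclusion.** The concern holds in limited form. At surplus sites the rule leaves the choice among patients with the same initial unspecified, and the caveats in 8.5 and 8.9 mention neither this nor the effect of roll-forward. The actual size cannot be determined from the documents. The illustrations rest on an assumed twofold surplus, assumed initials, wrap after Z and, for survival, perfect preference for the longest-surviving patient under an exponential model. On those terms the site-level excess in mean survival is at most about 20% or about 2%, depending on a detail the plan leaves open, and smaller after pooling.

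It would go too far to read this as showing that the study's survival or duration results will be biased by 20%, or that the design is invalid. Nothing in the documents shows how many sites will have surplus, or that abstractors would prefer particular charts. The point is that an avoidable, outcome-related selection step is left open and is inexpensive to close before abstraction begins.

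**What to change.** In 8.5, replace the letter rule for surplus sites:
- The site lists all eligible patients under sequential numbers in a fixed order, for example by date of starting the 2/1 schedule. That date exists both for patients who switched and for the Brazilian patients who started on it.
- The list stays at the site; only the count is reported, so no identifiers leave.
- The coordinating group returns a computer-generated random ordering, and the site abstracts in that order until its quota is met.
- The number eligible and the number sampled are recorded and reported per site.

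Update the matching limitation in 8.9 and the eCRF instructions. Every eligible patient at a site then has the same chance (10/20 = 0.50 in the example), whatever the surname.

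The cost is modest but real. Surplus sites must screen and list eligible patients before abstraction, which is more than the estimate they already give. Where the protocol has already been submitted, the edit needs ethics approval under 9.4. If an amendment is not practical, a sentence in the abstraction instructions that fixes the choice within a letter, the redraw and the step after Z would close the discretion, but would leave the roll-forward inequality. This is a cheap improvement, best made before the first surplus site starts, because discretionary selection cannot be undone later.

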8.6. Data Management

PPD will perform the analyses described in this proposal using Statistical Analysis Software (SAS) application housed on PPD secure, large-capacity, high-performance Linux mainframe. Experienced PPD programmers and analysts will perform all analyses. To ensure the integrity and quality of the study results, we will follow our programming validation life-cycle process for all analyses. This includes quality-checking programs, logs, and output for accuracy according to relevant standard operating procedures.

To ensure the integrity and quality of study results, PPD implements several practice standards for statistical programming, database management, and documentation for all projects involving databases analyses. The following 3 steps will be undertaken to achieve this high level of quality:

- Documentation of SAS programming;
- Validation of SAS programs;
- Database storage and retention.

8.6.1. Documentation of SAS Programming

To ensure smooth transitions of analytic methods and work among programmers, reviewers, and other project personnel, documentation of the following information will be created for each SAS program:

- Project name;
- Program name;
- Program purpose;
- Program author;
- Date the program was completed;
- Descriptions of subsequent changes and/or enhancements, with name of programmer and date for each.

This information will be incorporated into each program in the form of a header. In addition to documenting this information in a general program header, each program will include detailed comments throughout to describe the purpose and method of specific programming statements.

8.6.2. Validation of SAS Programs

In this section, we describe a variety of programming validation methods, including log review, review of data listings, and independent programming, which will be used to ensure that our SAS programs function as intended. The validation methods described in this section are not exhaustive, and additional measures will be implemented as appropriate.

8.6.3. Log Review

Programmers will review all SAS log files. This procedure is a widely accepted, basic level of program validation. The following issues must be addressed as part of a log review:

- No errors should appear in a log file.

PFIZER CONFIDENTIAL

- If warning messages or messages related to uninitialized variables are permitted in the log file, the programmer will document why they are permitted.
- The programmer will account for the number of observations reported at each executed data step, especially when the number of observations increases or decreases.
- The log file will contain all lines of the program as it was saved at the time of execution, and it will contain only those lines of code.

8.6.4. Review of Data Listings and Tables of Summary Statistics

Because an error-free log file does not necessarily demonstrate that a SAS program has functioned as intended, programmers will produce cell frequencies, means, and other summary statistics on specific data items to demonstrate that the program results are valid. When appropriate, we also will have a separate analyst review these listings independent of the programmer.

8.6.5. Independent Programming

For highly complex programming tasks, a second programmer will attempt (if necessary) to independently reproduce output generated by the initial programmer. If the outputs are equivalent, the test will be considered successful. If the outputs are not equivalent, the programmers will evaluate the differences and make appropriate corrections.

8.6.6. Validation Documentation

- For each SAS program used to produce final study outputs for presentation, PPD will complete and store a formal SAS validation document.

8.6.7. Case Report Forms (CRFs)/Data Collection Tools (DCTs)/Electronic Data Record

As used in this protocol, the term CRF should be understood to refer to either a paper form or an electronic data record or both, depending on the data collection method used in this study.

A CRF is required and should be completed for each included patient. The completed original CRFs are the sole property of Pfizer and should not be made available in any form to third parties, except for authorized representatives of Pfizer or appropriate regulatory authorities, without written permission from Pfizer.

To comply with privacy requirements, physicians (or the designated research team) will be abstracting the clinical and safety data directly from patients' medical records to the eCRF, and neither Pfizer nor PPD will have access to patients' medical records. To decrease chances of data-entry errors and resulting inaccuracies, data checks will be programmed into the eCRF, where possible, to improve the internal consistency of the data. Physicians (or the designated research team) will be able to make changes to the data in the eCRF before it is submitted, and any requests for corrections to entries made in the eCRFs will be dated and explained (if necessary).

PFIZER CONFIDENTIAL

8.6.8. Database Storage and Retention

To enable evaluations and/or inspections/audits from regulatory authorities or Pfizer, the investigator agrees to keep records, including the identity of all participating patients (sufficient information to link records, eg, CRFs and hospital records), copies of all CRFs, safety reporting forms, source documents, and adequate documentation of relevant correspondence (eg, letters, meeting minutes, and telephone call reports). The records should be retained by the investigator according to local regulations or as specified in the clinical study agreement, whichever is longer. The investigator must ensure that the records continue to be stored securely for so long as they are retained.

If the investigator becomes unable for any reason to continue to retain study records for the required period (eg, retirement, relocation), Pfizer should be prospectively notified. The study records must be transferred to a designee acceptable to Pfizer, such as another investigator, another institution, or to an independent third party arranged by Pfizer.

Study records must be kept for a minimum of 15 years after completion or discontinuation of the study, unless specific Pfizer protocols or PPD policies explicitly prohibit this. If any data-cleaning activities or other analyses need to be repeated for any reason, this retention procedure will allow quick and efficient access to the data sets. If requested by Pfizer, the raw analytical files will be provided to Pfizer.

[figure not shown]
The investigator must obtain Pfizer's written permission before disposing of any records, even if retention requirements have been met.

